9.4 Interim Analyses and Stopping Rules

During the study, we will not perform any interim analyses, which are analyses that are done before the end of the study to check the progress and results. We will only do interim analyses if the Institutional Review Board (IRB) requests them. If any SAEs occur during the study, we will report them to the IRB as quickly as we can follow their instructions. SAEs are events that are harmful or life-threatening to the subjects and that are unexpected, serious, and related to the intervention that we are testing. The IRB will have the responsibility to review the study and recommend whether to terminate it or not based on its assessment of the risks and benefits for the subjects. The IRB will do this if it determines that the subjects are exposed to more harm than good at any point during the study.

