7.1 Specification of Safety Parameters

Participants were required to take solifenacin and high-dose VDS as part of the study. Anticholinergic side effects, including dry mouth, blurred vision, constipation, and nausea, among others, may occur due to solifenacin use. If any of these symptoms occur, the medication will be discontinued, and the participant will be removed from the study. Over-supplementation of vitamin D can lead to symptoms of vitamin D toxicity, including anorexia, nausea, diarrhea, constipation, irritability, and somnolence. Any occurrence of these adverse drug reactions or serum vitamin D levels exceeding 100 ng/mL will be evaluated as unsafe.

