7.3 Adverse Events and Serious Adverse Events

The study may result in adverse events related to medication side effects of solifenacin and high-dose VDS. Adverse events and serious adverse events will be classified based on the severity and intensity of the side effects.

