7.4 Reporting Procedures

In the event of any adverse event, investigators will be notified within 24 hours.

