9.5.3 Safety analysis

The safety analysis will be performed using the Safety Analysis Set, which will assess treatment-emergent adverse events (TEAEs). Detailed recordings of all severe adverse events and TEAEs leading to discontinuation from the study will be included. Changes in clinical laboratory parameters and vital signs at each scheduled time point from baseline will be summarized according to treatment groups.

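### Section 9.4 counts an event as an SAE only if it is also unexpected and related, so other serious events fall outside the plan's only event-driven report to the IRB

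*Combined protocol and SAP*

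**What the plan says.** Section 9.4 gives the plan's only definition. To be an SAE, an event must be harmful or life-threatening, and it must also be "unexpected, serious, and related to the intervention that we are testing". Just before this, the section sets the reporting duty: "If any SAEs occur during the study, we will report them to the IRB as quickly as we can follow their instructions". The same section gives the IRB its role: "The IRB will have the responsibility to review the study and recommend whether to terminate it or not". No interim analysis is planned unless the IRB asks for one.

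Three other sections bear on the same events:

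- Section 7.3: "Adverse events and serious adverse events will be classified based on the severity and intensity of the side effects".
- Section 7.4: "In the event of any adverse event, investigators will be notified within 24 hours".
- Section 9.5.3: "Detailed recordings of all severe adverse events and TEAEs leading to discontinuation from the study will be included".

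Section 7.1 names in advance the effects that might follow from each drug. For vitamin D: "Over-supplementation of vitamin D can lead to symptoms of vitamin D toxicity, including anorexia, nausea, diarrhea, constipation, irritability, and somnolence". For solifenacin it lists anticholinergic effects such as constipation and nausea. Section 7.6, on safety monitoring, only refers back to the preceding text.

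**The concern.** Seriousness, relatedness and expectedness are three separate properties of an adverse event. Seriousness describes the outcome for the patient, relatedness is a causal judgement, and expectedness is a comparison with what is already known. Section 9.4 makes all three conditions of being an SAE and then uses that label to decide what the IRB is sent.

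At stake is the information on which the IRB weighs harm against benefit. Serious cases of foreseeable drug effects matter to that judgement, and so do serious events in every arm, whatever a local assessor thinks of their cause. The trial enrols children, plans no interim analysis and describes no separate safety board, so the content of the IRB report matters more than it otherwise might.

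**Working it through.** No arithmetic applies: the documents give no SAE rate and no stopping boundary. The check sets the sections side by side.

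**Step 1: which serious events meet the definition.** The conditions in 9.4 are joined by *and*, so all must hold. For an event that is serious and harmful or life-threatening:

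| | Unexpected | Expected |
|---|---|---|
| Judged related | SAE, reported to the IRB | Not an SAE |
| Judged unrelated | Not an SAE | Not an SAE |

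One of the four combinations triggers a report. This counts categories and says nothing about the share of events in each.

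**Step 2: whether the expected column can be filled.** The plan does not define expected. Section 7.1 lists anticipated effects for both drugs, and constipation and nausea appear in both lists. A child admitted to hospital with one of these could be read as having an expected event, and so no SAE.

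**Step 3: which arms are covered.** Relatedness is to the intervention being tested, in the singular. Section 9.2 uses the label of new intervention for high-dose VDS plus SU. Sections 3 and 5.1 call all three arms intervention groups. Section 7.3 ties adverse events to side effects of solifenacin and high-dose VDS. Coverage could therefore be the VDS arm alone, the two drug arms, or all three. The text does not settle it.

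**Step 4: whether another section defines serious.** In 9.4 the word appears inside the definition of a serious adverse event, which is circular. Section 7.3 can be read in two ways: severity separates SAEs from other adverse events, or each kind is graded for severity. On neither reading is an outcome criterion stated, such as death, hospitalisation or lasting disability. Section 9.5.3 speaks of severe events, which is a different property.

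**Step 5: whether another route reaches the IRB.**

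| Section | Route | Triggered by an event? | Limit |
|---|---|---|---|
| 9.4 | SAE report | Yes | Narrow definition; no reporting time stated |
| 9.4 | Interim analysis | No | Only if the IRB asks |
| 11.5 | Monitoring under the IRB | No | Inspection of SAE records inherits the 9.4 definition |
| 12 | Audit by the IRB auditor | No | No timing stated |
| 7.4 | 24-hour notice of any adverse event | Yes | Goes to investigators |
| 10.1 | Regular review of adverse events | No | Done by the research team |

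Only the first row is both event-driven and addressed to the IRB.

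**The case against.** The strongest reply is that the IRB is not cut off. Section 11.5 makes it responsible for monitoring, including follow-up, protocol compliance and data quality. Section 12 provides for an audit covering all study documents, and 9.4 lets the IRB request an interim analysis. This stands, and a reader who inferred that such events could never reach the IRB would go too far. These routes are not substitutes for an event report, for the reasons in the route table, and the IRB may have no signal that prompts it to ask.

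Individual children also have protection. Investigators hear of any adverse event within 24 hours, section 8 provides for discontinuation, and the research team reviews adverse events regularly. That stands too, but it does not put the events before the body that judges the trial as a whole.

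On expectedness, a listed symptom that became serious might still be called unexpected in its severity. The plan does not exclude that reading, so the point is that such a case *could* be left out, not that it must be.

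Four further inferences are tempting, and the documents do not support them:

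- *That the IRB alone can stop the trial.* Section 11.4 also names other government agencies.
- *That relatedness is judged by a clinician who knows the arm.* No section says who judges it, and the design is observer-blind.
- *That SAE counts in the analysis are biased between arms.* Section 9.5.3 applies no filter for relatedness or expectedness to the safety analysis.
- *That almost no SU-alone event could qualify, or that the 9.4 definition removes that arm from the safety analysis.* SU alone is called an intervention group, so its status under 9.4 is unclear rather than excluded. Its loss from the safety analysis comes from 9.3.3, which requires at least one dose of study drug. That is a separate matter, and the change proposed here would not repair it.

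**Conclusion.** The concern holds in a limited form. As written, 9.4 leaves serious events that are expected or judged unrelated outside the plan's only event-driven report to the IRB. It does not settle whether solifenacin-arm or SU-arm events qualify, and no section states what makes an event serious. This is a stated rule that works against its own purpose, not merely missing detail, so it should be corrected.

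The size cannot be put in numbers. The plan is to recruit 97 children per group, about 300 in all, but it gives no expected SAE rate and no split by relatedness or expectedness.

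The conclusion assumes that 9.4 is applied literally and that no reporting rule exists outside these documents. IRB instructions asking for all serious events would narrow the gap in practice, but the plan does not set out any such instructions.

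**What to change.** - In 7.3 and 9.4, define an SAE by stated outcome criteria (for example death, a life-threatening event, hospitalisation or lasting disability), regardless of relatedness or expectedness.
- Record relatedness, expectedness and severity as three separate fields for each event.
- Report SAEs from all three arms to the IRB, within a stated time and listed by arm. Keep unexpected and related only as a label for the subset that is reported on an expedited basis.
- Reconcile serious and severe across 7.3, 9.4 and 9.5.3, so that 9.5.3 presents serious events as well as severe ones.

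The cost is wording in three sections, the added fields on the adverse event form, and a few more reports to the IRB. No treatment rule, sample size or efficacy analysis changes.

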9.5 Outcomes and data Analyses

We will employ diverse measures to describe the characteristics of our data, depending on their nature. For numerical data that are continuous and can take any value within a range, we will use the mean (the arithmetic average of all values), the SD (a measure of how much the values deviate from the mean), the median (the central value when the data are sorted from the lowest to the highest), and the interquartile ranges (IQRs) (the range containing the middle 50% of data). For non-numerical data that are categorical and can belong to multiple groups or categories, we will use the frequency (the number of occurrences for each category) and the percentile (the proportion of data that falls below a specific value or category).

We will examine our data for any outliers or missing values that could influence our analysis. Outliers refer to values that differ significantly from the majority of the data and may indicate errors or exceptional cases, while missing values are data points that are unavailable or not recorded. Although we will employ effective data collection and management practices, missing values may still occur due to various factors.

To estimate the missing values for continuous data, we will use multiple imputation. This approach replaces the missing values with plausible estimates based on the other available data. We will assume that the missing values are missing completely at random, meaning that their occurrence does not depend on any variable, including their value. We will also conduct a sensitivity analysis to determine if the missing values affect our results or conclusions.

9.5.1 Primary Outcome

The study aims to determine the primary outcomes of urinary frequency among three groups of participants. The frequency of urination will be recorded at three different points in time, i.e., when the participants enroll in the study, four weeks after starting the treatment, and eight weeks after starting the treatment. We will compare the frequency of urination between the groups at each time point, and assess changes in urination frequency from enrollment to four weeks after starting treatment. To record urinary frequency, we will use a bladder diary, and these outcomes will be considered continuous variables, with any positive integer value within a specified range.

To analyze the data, we will use the intention-to-treat approach to avoid bias from factors such as dropout or crossover. We will also handle missing data before analysis. Statistical tests will be applied to compare the groups based on data distribution and variance, which affects the reliability of results. For normally distributed data with homogeneous variance, we will use ANOVA, followed by post-hoc comparisons and Bonferroni correction to reduce Type I errors. We will report data changes using mean and SD and differences between groups using point estimation and 95% confidence intervals (95%CI).

For non-normally distributed data with heterogeneous variance, we will use the Kruskal-Wallis test to compare groups. Post-hoc comparisons between groups will be done using the Wilcoxon rank sum test, and p-values will be adjusted by Bonferroni correction. Data changes will be reported using median and IQRs, and differences between groups using the Hodges-Lehmann (HL) estimate of location shift and 95% confidence intervals (95%CI). P-values will also be adjusted for multiple comparisons to avoid false positives, and a two-tailed P-value less than .05 will be considered statistically significant.

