9. STATISTICAL CONSIDERATIONS

9.1 General Design Issues

Objective: The aim of this randomized controlled trial is to examine the effectiveness and safety of high-dose VDS plus SU for managing OAB-dry symptoms in pediatric patients with low vitamin D levels (<35ng/mL).

Specific Aim 1: The main outcome is the difference in post-treatment improvement between children who receive high-dose VDS plus SU and those who receive solifenacin plus SU or SU monotherapy for OAB-dry symptoms. The study expects that high-dose VDS plus SU will lead to more improvement than SU monotherapy and solifenacin plus SU. Furthermore, SU monotherapy will result in less improvement than solifenacin plus SU.

Specific Aim 2: The secondary outcome is the safety profile of high-dose VDS plus SU for OAB-dry symptoms in pediatric patients. The study anticipates that the safety profile of high-dose VDS plus SU will be similar to that of solifenacin plus SU or SU monotherapy at follow-up.

The study design is an 8-week randomized controlled trial, and all treatments will be administered in a group setting. Pediatric patients with OAB-dry symptoms will undergo 8 weekly sessions of high-dose VDS plus SU, solifenacin plus SU, or SU monotherapy. Independent assessors will evaluate the patients before the treatment, at mid-treatment (4-week follow-up), and at the 8-week follow-up to test the expectations. To account for attention, time, and group effects, all SU sessions will be administered in a group setting.

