We also measured how much their symptoms bothered them and how their healthrelated QoL was affected by their condition using the QoL score questionnaire. The QoL score is a tool that measures how satisfied participants are with their health and well-being. We also asked participants to rate how much they improved and how satisfied they were with the treatment using validated tools. The results of our preliminary study were positive and showed that our new intervention was promising. This encouraged us to continue with our main trial and test our intervention further. We created and finalized the study protocol, which is the document that describes the details and procedures of our study. We developed all data collection tools and forms, which are the tools and documents that we use to collect and record data from participants. We obtained IRB approvals at the National Clinical Research Center for Child Health and Disease (Chongqing, China), which are approvals from a committee that oversees the ethical aspects of our study and protects the rights and welfare of participants. We offered standard training to all coordinators and interventionists, who are the people who help us run the study and deliver the intervention to participants. Our preliminary data helped us to determine how many participants we needed for our main trial.

The primary outcome in our study will be the change in median voiding frequency from enrollment to 4-week follow-up and 8-week follow-up. In our previous feasibility study, the mean number of voids per day was 16.0 (SD, 5.0) at enrollment. We used the power analysis program PASS 15.0 to estimate the sample size of this randomized controlled trial. A sample size of 87 participants per group was needed to detect a difference of 1.5 voids per day between groups at the 0.05 level of significance, achieving more than 95% power, assuming an estimated SD of 5.0 after 8 weeks of treatment. We plan to recruit 97 participants per group, anticipating a 10% follow-up attrition, to ensure adequate power for the trial, for a total of about 300 participants. Our sample size estimations are supported by our previous trial.

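### Section 9.2 makes the changes in voiding frequency to weeks 4 and 8 primary, but 9.5.1 analyses the change to week 4 only, and no section names the deciding endpoint or the adjustment family

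*Combined protocol and SAP*

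**What the plan says.** Section 9.2 defines the endpoint: "The primary outcome in our study will be the change in median voiding frequency from enrollment to 4-week follow-up and 8-week follow-up". Its sample size is set for one between-group difference, "A sample size of 87 participants per group was needed to detect a difference of 1.5 voids per day between groups", "assuming an estimated SD of 5.0 after 8 weeks of treatment".

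Section 9.5.1 sets out the primary analysis. Frequency is recorded at enrollment, week 4 and week 8. The plan then states "We will compare the frequency of urination between the groups at each time point", and that it will "assess changes in urination frequency from enrollment to four weeks after starting treatment". It tests by ANOVA, "followed by post-hoc comparisons and Bonferroni correction to reduce Type I errors", or by Kruskal-Wallis and Bonferroni-adjusted Wilcoxon tests. A closing sentence says that P-values are also adjusted for multiple comparisons, without saying which comparisons.

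Section 9.1 describes the aim: "The main outcome is the difference in post-treatment improvement between children who receive high-dose VDS plus SU". It schedules assessments before treatment, "at mid-treatment (4-week follow-up), and at the 8-week follow-up to test the expectations". Section 9.5.2 follows the secondary outcomes to both 4 and 8 weeks.

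**The concern.** The section that defines the primary outcome and the section that analyses it disagree. Followed literally, 9.5.1 never tests one of the two changes that 9.2 calls primary, and it is the change at the end of the eight-week treatment, where the rest of the text points.

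Restoring the missing words would not settle the matter. There would still be two changes and several level comparisons under the primary heading, with no statement of which result decides the trial. Success could be claimed on the week-4 change, the week-4 level or the week-8 level, each time citing the plan. The choice could then be made after the results are seen, and the nominal 0.05 would not necessarily hold.

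**Working it through.** **1. The passages side by side**

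| Section | Week-4 change | Week-8 change | Levels | Named as deciding? |
|---|---|---|---|---|
| 9.2 (definition) | primary | primary | not mentioned | no |
| 9.5.1 (analysis) | assessed | not mentioned | each time point | no |
| 9.1 (aim) | week 4 is mid-treatment | implied by post-treatment improvement | not mentioned | no |
| 9.5.2 (secondary outcomes) | yes | yes | compared | not applicable |

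**2. The plan's own sample size**

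Inputs from 9.2: 87 per group, difference 1.5, SD 5.0, alpha 0.05, power above 95%. The documents give neither the test nor the pattern of means. Assume one three-group ANOVA with means 0, 1.5 and 3.0. The noncentrality is n × Σ(mean − grand mean)² / SD² = 87 × (2.25 + 0 + 2.25) / 25 = 15.66. Power is 95.05% at 87 and 94.8% at 86, so 87 reproduces. With 10% attrition, 87 / 0.9 = 96.7, or 97. On this assumed pattern the figure fits one test at the full 0.05, with no allowance for a second primary time point.

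**3. False-positive rate if any one test may count**

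Simulation with no treatment effect: 3 arms of 87, normal data, 40,000 trials per row. A false claim needs the three-group F test at 0.05 and at least one pair at 0.05/3. The documents give no visit correlations, so all of them are assumptions. Let b be the correlation of each visit with baseline and w the correlation between weeks 4 and 8. The correlation between the two changes is (1 + w − 2b) / (2 − 2b). If w = b this is 0.5 whatever b is, so b and w must be varied separately.

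| b | w | Correlation of changes | Week-8 change alone | Either change (9.2) | Week-4 level, week-8 level or week-4 change (9.5.1) | Both changes required |
|---|---|---|---|---|---|---|
| 0.3 | 0.3 | 0.50 | 4.1% | 7.7% | 11.4% | 0.7% |
| 0.7 | 0.7 | 0.50 | 4.3% | 7.8% | 10.8% | 0.6% |
| 0.5 | 0.7 | 0.70 | 4.1% | 6.9% | 10.4% | 1.2% |
| 0.7 | 0.9 | 0.83 | 4.2% | 6.5% | 9.9% | 1.9% |
| 0.3 | 0.9 | 0.93 | 4.3% | 5.9% | 9.4% | 2.7% |

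The enrollment-level comparison is left out because it cannot show a treatment effect. The Kruskal-Wallis and Wilcoxon route, run on mildly right-skewed data with w = b, gives nearly the same rates: 4.0-4.3%, 7.6-7.9% and 10.5-11.0% for the first three rate columns.

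**4. False-positive rate if the adjustment spans the whole set**

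With pairs tested at 0.05/6 for the two changes in 9.2, or at 0.05/9 for the three tests in 9.5.1, the rate is about 3-4% over the same correlations.

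**The case against.** The strongest reply is that this is a slip of the pen. Section 9.5.1 records frequency at week 8, compares groups there, and speaks of reporting changes without a time limit. Section 9.2 names both changes, and 9.5.2 uses both time points. That stands as the likely cause: a reader should not infer that the sponsor meant week 4 to decide, or that week-8 evidence is dropped. What remains is that the week-8 level is not the change that 9.2 defines, and mending the sentence still leaves the deciding test unnamed.

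A second reply is that the plan already adjusts P-values, and that its closing sentence can be read as going beyond the three pairs. A reader might infer from the table above that the trial has an inflated error rate. The documents do not support that as a fact, because the inflation needs two readings that no section states. The demonstrated defect is an undefined family.

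Two further inferences go too far. Section 6.2.5 mentions urgency beside primary frequency, but the adjective can belong to frequency alone, and 9.2, 9.5.1 and 9.5.2 consistently make frequency primary and urgency secondary. Nor does this point show the sample size to be wrong: 87 and 97 reproduce for a single endpoint under the pattern assumed above.

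**Conclusion.** The point holds as a contradiction between 9.2 and 9.5.1, together with an unnamed deciding endpoint and an undefined adjustment family. It concerns the primary analysis and must be fixed, even though the cause is probably clerical.

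The size is conditional. If any one test counts and Bonferroni covers only the three pairs, the false-positive rate is about 6-8% for the set in 9.2 and about 9-11% for the set in 9.5.1, against about 4% for the week-8 change alone. This assumes correlations of 0.3 to 0.7 with baseline and 0.3 to 0.9 between weeks 4 and 8. There is no inflation if the adjustment covers the whole set (about 3-4%) or if both time points must succeed (about 1-3%). The text commits to neither.

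**What to change.** In 9.2 and 9.5.1, name the change in voiding frequency from the run-in diary baseline to week 8 as the single primary endpoint. Test it with one three-group test at 0.05 (ANOVA or Kruskal-Wallis under the existing rule), followed by Bonferroni-adjusted pairwise comparisons, and state that the family is those three pairs. Make the week-4 change and the levels secondary. If the sponsor prefers both time points as primary, say whether both must succeed or how alpha is split. As a wording note, rephrase 6.2.5 so that urgency is clearly secondary.

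The cost is wording only. The schedule in 6.1 already collects the diary in the run-in and at weeks 4 and 8. Week-4 results would no longer count as primary. The sponsor should also confirm that SD 5.0 applies to the change. If it is the SD of the level at both visits, the SD of the change is 5.0 × √(2 × (1 − r)), where r is the correlation of baseline with week 8: 5.9 at r = 0.3, 5.0 at 0.5 and 3.9 at 0.7. Splitting alpha equally instead would lower power at 87 per group from 95.0% to 91.4% and need 100 per group for 95%, under the assumed 0, 1.5, 3.0 pattern. Other power questions belong in a separate point.

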6.2.2.2 Baseline assessment

All participants will have a 7-day run-in period during which children are asked to carefully record their OAB-dry symptoms. The purpose of this run-in period is to establish a baseline for evaluating the effect of the intervention measures investigated.

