For data that are not normally distributed or have heterogeneous variance, we will use the Kruskal-Wallis test to compare the groups. The Kruskal-Wallis test is suitable for comparing three or more groups with continuous data that do not meet the assumptions of ANOVA. We will report the data and their change using median and IQRs, which show the middle and range of the data. Additionally, we will perform posthoc comparisons between groups using the Wilcoxon rank-sum test, which can compare two groups with continuous data that do not meet ANOVA assumptions. We will report these comparisons using the HL estimate of location shift and 95% confidence intervals, which show how much one group differs from another group in terms of location or central tendency. We will also report an adjusted P value for each comparison.

We will assess and compare how participants perceive their improvement from enrollment in the study to 4 and 8 weeks after treatment initiation. This subjective outcome reflects how participants feel about their condition and treatment, which we will measure using a rating scale with categories such as much better, better, about the same, or worse. Since this is non-numerical, ordered categorical data, we will use the PP analysis set to analyze the subset of subjects who adhered to the protocol without major deviations. We will apply the Kruskal-Wallis test to compare groups based on their ratings of improvement at different time points, reporting the data using frequency and percentile. We will use a two-tailed P-value to determine statistical significance, setting a cutoff of less than .05, unless specified otherwise.

Additionally, we will record and compare participant satisfaction with the current treatment and their willingness to receive another therapy. This dichotomous outcome measures whether participants answered yes or no to whether they would like to receive another therapy. We will use the PP analysis set and the chi-square test to compare the groups based on their responses at different time points. We will report the data using frequency and percentile, and consider a P-value of less than .05 to be statistically significant, unless specified otherwise.

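### The primary analysis in 9.5.1 does not adjust for baseline voids, gives no test for two of four data patterns, and lets the data decide which treatment effect is reported

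*Combined protocol and SAP*

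**What the plan says.** Section 9.5.1 states: "We will compare the frequency of urination between the groups at each time point". It adds that the trial will "assess changes in urination frequency from enrollment to four weeks after starting treatment". The test depends on the data:

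- "For normally distributed data with homogeneous variance, we will use ANOVA", with Bonferroni-corrected post-hoc comparisons, means and SDs, and point estimates with confidence intervals.
- "For non-normally distributed data with heterogeneous variance, we will use the Kruskal-Wallis test to compare groups", with Wilcoxon post-hoc tests, medians and IQRs, and the Hodges-Lehmann shift.

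No normality or variance check is named, and no threshold is given. For secondary outcomes, section 9.5.2 joins the two conditions differently: "For data that are not normally distributed or have heterogeneous variance, we will use the Kruskal-Wallis test to compare the groups".

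Section 6.2.2.2 says of the 7-day diary before treatment: "The purpose of this run-in period is to establish a baseline for evaluating the effect of the intervention measures investigated". No covariate model appears anywhere in section 9.

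Section 9.2 defines the endpoint: "The primary outcome in our study will be the change in median voiding frequency from enrollment to 4-week follow-up and 8-week follow-up". It then sizes the trial on a mean and SD: "the mean number of voids per day was 16.0 (SD, 5.0) at enrollment", an SD of 5.0 after 8 weeks, and a difference of 1.5 voids per day.

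**The concern.** There are three linked weaknesses in the primary analysis.

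1. **Baseline.** A full week of baseline voids is collected, but it enters only through change scores. A change score uses the baseline less efficiently than a covariate does.
2. **Gap in the rule.** In 9.5.1 both conditions must hold for either branch to apply. Two of the four combinations therefore have no primary test, and someone would have to choose one after seeing the data.
3. **Moving target.** The branch selects the estimator as well as the test. The rule can be applied visit by visit, so weeks 4 and 8 could be reported on different scales. The documents do not settle the target either: 9.2 says median but sizes on a mean, and it names weeks 4 and 8, while 9.5.1 names change to week 4 only.

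**Working it through.** **Inputs.** From 9.2: 87 per group analysed, 97 recruited, difference 1.5, SD 5.0, more than 95% power. From 9.5.1: two-sided 0.05 and Bonferroni correction, so 0.05/3 = 0.0167 for three pairs. Assumed, because the documents do not give it: the baseline-to-follow-up correlation r, with SD 5.0 at both times.

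**The plan's own figure.** A one-way ANOVA F test with means 0, 1.5 and 3.0 (the even spacing is an assumption) has noncentrality 87 × (1.5² + 0 + 1.5²)/25 = 15.66. Power is 0.9505, and 87 is the smallest group size reaching 95%. Then 87/0.9 = 96.7, rounded up to 97. The figure reproduces, and it uses no covariate.

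**Baseline adjustment.** Residual SDs:
- level: 5
- change: 5√(2(1−r))
- ANCOVA: 5√(1−r²)

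Since 2(1−r) − (1−r²) = (1−r)² ≥ 0, ANCOVA is never less precise than change, and it is never less precise than level. Power for one 1.5-void pair (noncentral t, 87 per arm, 0.0167):

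| r | SD level / change / ANCOVA | Power level / change / ANCOVA |
|---|---|---|
| 0.3 | 5.00 / 5.92 / 4.77 | 33% / 23% / 37% |
| 0.5 | 5.00 / 5.00 / 4.33 | 33% / 33% / 45% |
| 0.7 | 5.00 / 3.87 / 3.57 | 33% / 56% / 64% |
| 0.8 | 5.00 / 3.16 / 3.00 | 33% / 76% / 81% |

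For the omnibus test, r = 0.5 raises the noncentrality to 15.66/0.75 = 20.88 and power from 95.0% to 98.8%.

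**How often the rule assigns no test.** The checks are assumed: Shapiro-Wilk on pooled residuals and median-centred Levene, each at 0.05. Simulation used 87 per arm, baseline mean 16 (SD 5), follow-up mean 12, r from 0.3 to 0.7, and 1,000 or 2,000 runs per setting.

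| Follow-up levels | SDs 5/5/5 | 5/4/4 | 5/4/3 |
|---|---|---|---|
| Normal | 7–10% | 47–49% | 77–79% |
| Gamma | 95–97% | 56–60% | 7–9% |

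For change scores the shares were 9–26% (normal) and 25–47% (gamma). A separate simulation with Shapiro-Wilk applied per group and means 16, 14.5 and 13 gave 17% (normal, equal SDs), 40% (normal, SDs 5/4.5/4), 91% (gamma, equal SDs) and 68% (gamma, constant coefficient of variation).

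**What the Kruskal-Wallis branch tests.** Its assigned case is non-normal with unequal variances. With all means equal to 12, 97 per arm and 4,000 runs, Kruskal-Wallis rejected at the 0.05 level as follows:

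| Follow-up levels | SDs 5/4/3 | SDs 6/4/3 |
|---|---|---|
| Normal | 5% | 6% |
| Plain gamma | 10% | 15% |
| Shifted gamma, shape 4 | 12% | 16% |
| Shifted gamma, shape 2 | 21% | 31% |
| Shifted gamma, shape 1 | 46% | 60% |

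For gamma change scores (r = 0.5, 87 per arm, SDs 5/5/5, 5/4/4 and 5/4/3) the rates were 5%, 6% and 5%.

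**The case against.** **Adjustment is an efficiency preference, and change scores already use the baseline.** This is correct, and no bias is alleged. The gain is small against levels at low r (4 points at r = 0.3) and against change at high r (5 points at r = 0.8). The low pairwise power is mainly a sample-size matter that ANCOVA only eases. But no single unadjusted choice does well across the range of r, whereas ANCOVA is at least as precise as both.

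**The gap is probably a drafting slip.** It probably is, since 9.5.2 covers all four patterns and one word in 9.5.1 would close the gap. But 9.5.2 governs secondary outcomes only, and the one-word change leaves the switch of estimator in place. The 7% to 97% range is wide and depends on the assumed checks, so it shows that the gap can readily be met, not how often it will be. In the largest case, gamma with equal SDs, Kruskal-Wallis behaves properly (about 5% rejection).

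**The high Kruskal-Wallis rates are stress cases.** This stands. The 46% and 60% need strong skewness and unequal SDs that the documents do not report. They are not false positives for medians: the shape-1 medians at SDs 5/4/3 are about 10.5, 10.8 and 11.1. They are errors only for a mean target, and change scores stay at 5% to 6%. This shows why the target must be stated.

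**Analysts are blinded.** Section 6.2.3 conceals allocation from statisticians and limits the analyst to coded data. That reduces selective choice, but it neither supplies the missing test nor fixes the estimand.

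**Conclusion.** The concern holds and should be corrected. What can be read directly from the text needs no assumption: there is no baseline covariate, two patterns have no primary test, and 9.2 and 9.5.1 disagree on median against mean and on which visits count. The sizes rest on assumptions about r, equal SDs at baseline and follow-up, the distributions and the checks. On those, adjustment adds 4 to 48 percentage points of pairwise power against levels (37 − 33 at r = 0.3; 81 − 33 at r = 0.8) and 5 to 14 against change (81 − 76 at r = 0.8; 37 − 23 at r = 0.3). No power loss is attributed to the rank test itself, and the planned 87 per group is not disputed here.

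**What to change.** Replace the branching rule in 9.5.1, and for continuous outcomes in 9.5.2, with one model fixed in advance:

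- Regress mean daily voids at follow-up on treatment group and run-in baseline voids, or use a repeated-measures version with weeks 4 and 8. Choose one and write it down.
- Use heteroscedasticity-robust standard errors, with Bonferroni-adjusted pairwise contrasts and confidence intervals.
- State that the estimand is a difference in means and name the primary visit. The sample size points to week 8.
- Bring the median wording in 9.2 and the week-4-only change in 9.5.1 into line with that choice.
- Keep Kruskal-Wallis and Hodges-Lehmann as a sensitivity analysis.

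If the branches are kept, the minimum is to join the Kruskal-Wallis conditions in 9.5.1 with *or*, as 9.5.2 does, and to name the normality and variance checks with their thresholds. That closes the gap but leaves the estimand dependent on the data.

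The cost is SAP wording and slightly more analysis work. The baseline diary is already collected.
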